5.1 Participant Inclusion Criteria

Participants must meet all the inclusion criteria to be eligible to participate in the study. The criteria include:

- 1) Between 15 and 18 years of age, have not yet graduated from high school OR still living with caregivers
- 2) Diagnosed with moderate or complex structural CHD
- 3) Lives within 120 miles of NCH
- 4) Able to complete an exercise stress test on a treadmill

5.2 Participant Exclusion Criteria

Participants meeting any of the exclusion criteria at baseline will be excluded from the study. These criteria include:

- 1) Do not speak and write proficiently in English
- 2) Have a diagnosis of a genetic syndrome (e.g., Downs, Marfans, Wolf-Parkinson-White)
- 3) Have cognitive impairments that would interfere with completion of study measures
- 4) Have been engaged in a formal exercise program within the past 6 months, including cardiac rehabilitation
- 5) Have undergone open-heart surgery or have had a valve replacement in the last 3 months
- 6) Are prohibited to engage in MVPA by their cardiologist
- 7) Are unable to complete a treadmill-based exercise stress test

After completing Phase 1, participants are approached for recruitment into Phase 2 unless they meet additional exclusion criteria, including:

- 8) Having contraindications for exercise based on an exercise stress test (e.g., exercise-induced arrhythmias or evidence of cardiac ischemia)
- 9) Exercising >60 min/day of MVPA per the accelerometer
- 10) Do not have internet access or a device for videoconferencing with a PA coach

5.3 Treatment Assignment Procedures

5.3.1 Randomization Procedures

The PI, study staff, and the research participant do not know the participant's arm designation until the envelope, which was prepared by the study statistician ([name]) is opened. Randomization is stratified by the number of minutes spent in MVPA per the accelerometer data in

Phase 1 (adolescents: <21 min/day of MVPA vs. \geq 21 min/day of MVPA; emerging adults: \leq 25 min/day of MVPA vs. \geq 26-59 min/day of MVPA) with randomly varying block sizes. Strata were based on the mean baseline levels of MVPA as reported in 2 studies of adolescents with CHD^{27,28} and 2 studies of emerging and middle-aged adults with CHD.^{30,32}

5.3.2 Reasons for Withdrawal

Study participation is discontinued under the following circumstances:

- If participant's cardiologist determines that he/she is no longer eligible for the study due to a change in his/her cardiac condition.
- The participant or the participant's legal guardian requests withdrawal from the study.
- Development or reveal of any exclusion criteria (e.g., need for cardiac surgery).

5.3.3 Handling of Withdrawals

If withdraw occurs because a participant's cardiologist determines that the participant should no longer be in the study due to a change in medical status or the participant and/or caregiver request to be withdrawn, participants are asked to complete the assessments if possible and are included in intent-to-treat analyses.

5.3.4 Termination of Study

Because the AHA and American College of Cardiology indicate that receiving an exercise stress test is a standard of care and that CHD survivors with moderate to complex disease should be engaged in routine PA as long as it is deemed safe,⁸ termination of the study due to the development of adverse events is not anticipated. There are several procedures aimed to rule out any participants who may be at an increased risk of an adverse event due to the intervention. First, participants' cardiologists are asked about the eligibility of each potential participant. Second, participants undergo a baseline exercise stress test, in part, to rule out any cardiovascular contraindications for PA. If limitations in PA exist, these are incorporated into the exercise prescription developed by the exercise physiologist who conducted the stress test, and the PA coaches work with participants on PA within the parameters of the exercise prescription. Participants' cardiologists have access to the results of the stress test, which are posted in participants' electronic medical record. However, the study will be terminated if the Data Safety Monitoring Board (DSMB) or IRB concludes, based on their findings, that termination is in the best interest of the participants.

5.4 Study Intervention Description

During the Phase 2 of the study participants are randomized into the comparison or intervention arm. Both the comparison and intervention arm participants receive a Fitbit and are asked to complete the interim (between weeks 8-12), post-intervention (between weeks 20-26), and 6-month follow-up assessments. In addition, the intervention group is asked to complete 8 videoconferencing sessions with a PA coach over 20 weeks (Sessions 1-4 occur weekly; Session 5 is in week 6; Session 6 is in week 8; Session 7 is in week 12; Session 8 is in week 20) with each session lasting approximately 20-30 minutes. Intervention participants who complete the protocol will also be invited to partake in a focus group after the post-intervention assessment has been completed to provide feedback on their study experiences. The topics for the intervention sessions focus on helping participants to:

- 1) Understand the benefits of MVPA, find physical activities they enjoy, and delineate pros and cons of engaging in MVPA using a non-judgmental stance (*Attitudes*)
- 2) Trouble-shoot engaging family and friends to be supportive of or engage in PA with the participant (*Subjective Norms*)
- 3) Find creative ways to incorporate more MVPA, resolve barriers to PA and promote efficacy for engaging in MVPA, and identify intrinsic rewards for accomplishing goals (*Perceived Control*)

All of the sessions contain a goal-setting component based on the exercise prescription the participant obtained from his/her exercise stress test. Participants receive text messages in between sessions, which contain motivational or encouraging content.

5.4.1 Session Description

Session 1 (Week 1)

Coaches inquire about participants' attitudes about PA and encourage them to get familiarized with their Fitbit.

Session 2 (Week 2)

Participants' are encouraged to discuss their knowledge about PA and to think about pros and cons for engaging in PA. Goals are set in collaboration with the participant, including increasing participants' PA frequency, duration, or intensity.

Session 3 (Week 3)

Coaches inquire about participants PA self-efficacy/perceived control by asking what gets in the way of engaging in activities that the participant enjoys and troubleshoot around controllable

barriers. Participants are also encouraged to try a new type of PA. Goals are set for increasing frequency, duration, or intensity when engaging in PA.

Session 4 (Week 4)

Coaches will inquire about participants PA subjective norms (e.g., “Have you talked with your caregivers/siblings/friends/cardiologist about being active?” “What do they think about you being active?”), and are encouraged to talk to family/friends/cardiologist about being active if they have not, as well as invite family/friends to join them in physical activities. Goals are set to increase frequency, duration, or intensity of PA.

Session 5 (Week 6)

Coaches promote participants’ independence by modeling the use of core concepts from the Theory of Planned Behavior learned in Sessions 1-4 with emphasis placed on managing barriers and promoting boosters to PA. Participants are encouraged to increase frequency, duration, or intensity of PA based on what they perceived as being the easiest to increase.

Session 6 (Week 8)

Coaches continue promoting participants’ independence by discussing the process of goal-setting, including making achievable goals and anticipating barriers. Participants are asked to set up his/her goals in respect to increase frequency, duration, or intensity of PA.

Session 7 (Week 12)

Coaches continue promoting participants’ independence by reflecting about their progress and discussing the process of setting long-term goals. Participants are encouraged to set new goals ever 2 weeks during the span between Session 7 and 8. Coaches help participants identify potential barriers to achieving their goals, as well as how they can continue to use their Fitbit for self-monitoring.

Session 8 (Week 20)

Coaches summarize the intervention, focusing on the participant’s successes and gains. Coaches will also inquire about participants’ motivation and promote maintenance.

5.5 Modification of Study Intervention

Modifications to the study intervention may occur if a participant experiences a change in their cardiac health during the course of the study and his/her cardiologist recommends an alteration in the participant’s exercise prescription.

5.6 Accountability Procedures for the Study Intervention

Individual and group supervision sessions are held for coaches to clarify study procedures, receive feedback on interactions with participants, and share ideas for ways to trouble-shoot around barriers to PA that participants broach during session. [name], who is familiar with the study but is not directly involved, as well as another study staff member, will listen to a random selection of 2 audiotaped sessions per participant and rated on their fidelity. Fidelity <90% triggers retraining of the interventionist as to the study materials.

5.7 Assessment of Subject Compliance with Study Intervention

Participant compliance in the intervention arm is monitored in two ways. First, participants are asked to wear a Fitbit, which is used by the coaches to assess the participants' engagement in MVPA. Coaches request that participants in the intervention arm sync their Fitbit each day so that coaches may monitor their PA levels and incorporate feedback during sessions. Participants' attendance at each session is documented. For those participants in the comparison arm, they are told to sync their Fitbit regularly upon first receiving the Fitbit, but are not contacted about the Fitbit again.

5.8 Concomitant Treatments

Given the primary and secondary outcomes of the study, participants who are currently or have engaged in a formal exercise program in the past 6 months, including cardiac rehabilitation, are not able to participate in the study. Engaging in sports during the study is not an exclusionary criterion.

6 STUDY SCHEDULE, STUDY PROCEDURES/ EVALUATIONS

6.1 Screening

Potential participants are identified through scheduled clinic appointments for the upcoming month. Study personnel first identify patients who meet the age criteria and then check the patient's medical record to verify their eligibility based on the inclusion and exclusion criteria. If a patient appears to be eligible the cardiologist confirms that they do not know of any reason the patient should not participate in this research, including limitations to engaging in MVPA. The patient and/or their caregiver(s) (or their legal guardian of record), if an adolescent, is then sent a letter from the attending cardiologist, notifying them about the study and that study personnel will be in contact.

6.2 Phase 1: Enrollment/Baseline (T1)

Once the participant, and the caregiver if the participant is an adolescent, have consented/assented, they are asked to complete an online questionnaire. The participant is also asked to undergo an exercise stress test and wear an accelerometer for 7 days. The stress test is completed at NCH within 3-4 weeks of recruitment and standardized feedback will be provided by an exercise physiologist, which includes their VO_{2max} . Once completed, participants are compensated \$100 for their time for the baseline assessment.

Baseline online questionnaire:

- Socio-demographics characteristics (participant & caregiver, if applicable)

- Benefits of PA⁵⁰ (participant)

- Subjective Norms survey⁵¹ (participant & caregiver, if applicable)

- Social Support for Exercise survey^{52,54} (participant)

- Barriers to Exercise survey⁵³ (participant)

- Self-Efficacy for Exercise Scale⁵⁴ (participant)

- Patient-Reported Outcomes Measurement Information System⁴⁵⁻⁴⁷ (participant & caregiver, if applicable)

- International Physical Activity Questionnaire^{48,49} (participant & caregiver, if applicable)

- Cardiac Anxiety Questionnaire⁵⁵ (participant)

- Modified Body Image Disturbance Questionnaire⁵⁶ (participant)

Family Environment Scale⁵⁸ (caregiver, if applicable)

Child Vulnerability Scale⁵⁷ (caregiver, if applicable)

VO_{2max}: VO₂ measurement is obtained via a graded exercise stress test on a treadmill. Exercise stress test results are used by the exercise physiologist to devise an exercise prescription that consists of recommendations for frequency, duration, intensity and type of PA. Exercise prescriptions are provided to participants if they qualify and enroll in Phase 2. Participants who are found to have an arrhythmia or show evidence of cardiac ischemia during exercise stress testing are immediately referred to their cardiologist for follow-up and are not be eligible for Phase 2.

MVPA and SB: Participants receive a triaxial accelerometer (ActiGraph, model wGT3X-BT), sensitive to movement in all directional planes, to measure the amount of time spent in sedentary, light, moderate, and vigorous PA. The accelerometer is worn around the waist for 7 days for at least 10 hours per day, only to be removed when showering or submerging in water (e.g., swimming). Participants will also complete self-monitoring PA logs in the case they cannot wear the accelerometer (e.g. swimming). If baseline accelerometer and self-monitor PA log data indicate that a participant averages at least 60 minutes of MVPA per day, they are not eligible for Phase 2.

Compensation: Caregivers are compensated \$20 after they complete the baseline surveys. Participants are compensated \$100 for completing the baseline survey, exercise stress test, and wearing the accelerometer for at least 4 days (1 weekend day, 3 weekdays), for at least 10 hours per day. Additionally, participants' parking and mileage to/from the hospital for the exercise stress test are reimbursed.

Contact and Scheduling. If the participant is eligible for the Phase 2, they are contacted by phone and asked to schedule a home visit, within 8 weeks from their exercise stress test, if interested in participating.

6.3 Phase 2: Enrollment in the RCT

Eligible participants from Phase 1 are met at their home (or the hospital if preferred) to receive their Fitbit and exercise prescription, which is based on the results of their stress test. After receiving the Fitbit and exercise prescription, the participant's arm designation is revealed by opening an envelope that has been prepared by the study statistician, [name]. Prior to opening the envelop, the study PI, study staff, and the participant are blind to the study arm designation.

6.4 Interim Assessment (between weeks 8-12)

Participants in both arms are asked to complete an interim assessment (between weeks 8-12), which includes:

Interim online questionnaire: Participants are asked to complete the same questionnaire that was completed at Baseline, with the exception of those in the comparison arm receiving questions about changes to their health since Baseline.

- Benefits of PA⁵⁰

- Subjective Norms survey⁵¹

- Social Support for Exercise survey⁵²

- Barriers to Exercise survey⁵³

- Self-Efficacy for Exercise Scale⁵⁴

- Patient-Reported Outcomes Measurement Information System⁴⁵⁻⁴⁷

- International Physical Activity Questionnaire^{48,49}

- Cardiac Anxiety Questionnaire⁵⁵

- Changes in Health

MVPA and SB: Participants wear an accelerometer again for the same period (7 days) as the Baseline assessment and complete self-monitoring PA logs in the case they cannot wear the accelerometer (e.g. swimming).

Compensation: Participants are compensated \$50 for completion of the interim assessment survey and wearing the accelerometer for at least 4 days (1 weekend day, 3 weekdays), for at least 10 hours per day.

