6.5 Post-Intervention (between weeks 20-26)

Participants in both arms are asked to complete a post-intervention assessment (between weeks 20-26), which includes:

Post-intervention online questionnaire: Similar items are included on the post-intervention questionnaire as with the baseline and interim assessment with the exception that participants and their caregivers, if applicable, are asked to rate the intervention on multiple dimensions.

- Benefits of PA⁵⁰ (participant)

- Subjective Norms survey⁵¹ (participant & caregiver, if applicable)

- Social Support for Exercise survey⁵² (participant)

Barriers to Exercise survey⁵³ (participant)
Self-Efficacy for Exercise Scale⁵⁴ (participant)
Patient-Reported Outcomes Measurement Information System⁴⁵⁻⁴⁷ (participant & caregiver, if applicable)
International Physical Activity Questionnaire^{48,49} (participant & caregiver, if applicable)
Cardiac Anxiety Questionnaire⁵⁵ (participant)
Family Environment Scale⁵⁸ (caregiver, if applicable)
Child Vulnerability Scale⁵⁷ (caregiver, if applicable)
Changes in Health (participant)
Post-Intervention Satisfaction (participant & caregiver, if applicable)

MVPA and SB: Participants wear an accelerometer again for the same measurement period (7 days) as in previous assessments and complete self-monitoring PA logs in the case they cannot wear the accelerometer (e.g. swimming).

VO_{2max}: VO₂ measurement is obtained again with a graded exercise stress test using a modified Bruce protocol. Participants who were found to have an arrhythmia or show evidence of cardiac ischemia during exercise stress testing will be immediately referred to their cardiologist for follow-up.

Compensation: Caregivers are compensated \$20 during the exercise stress test visit after they complete the post-intervention surveys. Participants are compensated \$100 for completion of the post-intervention survey, exercise stress test, and returning the accelerometer with at least 4 days (1 weekend day, 3 weekdays), for at least 10 hours per day of data. Additionally, participants parking and mileage to/from the hospital for the exercise stress test are reimbursed.

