6.6 Focus Groups (after post-intervention assessment)

Participants in the intervention arm are asked to partake in a focus group lasting approximately 1.5 hours, to discuss their experiences in the study. There will be 3-4 groups that meet via videoconferencing with 6-8 participants per group.

Compensation: Participants are compensated \$50 for being in the focus group.

6.7 6-Month Follow-up (between weeks 46-50)

Participants in both arms are asked to complete a 6-month follow-up assessment (between weeks 46-50), which includes:

6-month follow-up online questionnaire: Participants are asked to complete the same questionnaire that was completed at the interim assessment.

- Benefits of PA⁵⁰

- Subjective Norms survey⁵¹

- Social Support for Exercise survey⁵²

- Barriers to Exercise survey⁵³

- Self-Efficacy for Exercise Scale⁵⁴

- Patient-Reported Outcomes Measurement Information System⁴⁵⁻⁴⁷

- International Physical Activity Questionnaire^{48,49}

- Cardiac Anxiety Questionnaire⁵⁵

- Changes in Health

MVPA and SB: Participants wear an accelerometer again for the same measurement period (7 days) as in previous assessments and complete self-monitoring PA logs in the case they cannot wear the accelerometer (e.g. swimming).

Compensation: Participants are compensated \$75 for completion of the 6-month follow-up assessment survey and wearing the accelerometer for at least 4 days (1 weekend day, 3 weekdays), for at least 10 hours per day.

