7 ASSESSMENT OF SAFETY

7.1 Methods and Timing for Assessing, Recording, and Analyzing Safety Parameters

7.1.1 Adverse Events

Adverse Event

For the current study, an adverse event is an unanticipated change in physical symptoms that is (1) concerning to the participant and (2) results in seeking medical attention. We do not anticipate any severe medical adverse events due to study procedures. However, medical events that occur for participants during the course of the study are comprehensively documented, including events during the stress test, symptoms reported during the course of the intervention, dates and reasons for pauses in the study protocol due to symptom reporting, and determination of ability to proceed by participants' cardiologists. All unscheduled cardiology outpatient visits, visits to urgent care or the emergency department, unscheduled hospitalizations, or any other changes in health are documented. Both participants in the comparison and intervention arms are asked whether they sought medical attention in the aforementioned contexts during the interim and post-intervention questionnaires.

The current study has several procedures in place to reduce the likelihood of serious adverse events. Potential participants' cardiologists are notified prior to being recruited for the study and excluded if the cardiologist has communicated or documented any concerns about that adolescent engaging in MVPA. All participants undergo a baseline exercise stress test and are not approached for recruitment for Phase 2 if contraindications are detected in Phase 1. In the rare event that a participant has an acute medical event during the exercise stress test, appropriate hospital procedures are enacted, which include calling an emergency response team and immediate evaluation by a cardiologist. The same procedures used for patients undergoing exercise stress testing as part of a medical evaluation are initiated and followed. During the course of the intervention, if an adolescent reports cardiac symptoms that are concerning to the participant and are new since the last cardiac evaluation, PA coaches are trained to request that the adolescent tell his/her caregiver (if they haven't already done so) and contact their cardiologist. Adolescents and their caregiver have given the study PI, [name], permission to talk with the cardiologist in the

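### Section 6.4 gives the interim health-change questions to the comparison arm only, against Section 7.1.1 and its own item list; if followed, adverse-event capture would differ by arm

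*Combined protocol and SAP*

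**What the plan says.** Section 6.4 opens by covering everyone: "Participants in both arms are asked to complete an interim assessment (between weeks 8-12"). It then says the questionnaire repeats the baseline one, "with the exception of those in the comparison arm receiving questions about changes to their health since Baseline". The list of instruments beneath that sentence includes "Changes in Health" with no mention of arm.

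Section 6.5 (post-intervention) lists "Changes in Health (participant"), again for either arm.

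Section 6.7 (6-month follow-up) is addressed to both arms and defines its form by reference: "Participants are asked to complete the same questionnaire that was completed at the interim assessment". Its own list also includes the health-change item without restriction.

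Section 7.1.1 states: "Both participants in the comparison and intervention arms are asked whether they sought medical attention in the aforementioned contexts during the interim". That sentence goes on to name the post-intervention form as well. The same section defines the event of interest: "an adverse event is an unanticipated change in physical symptoms that is (1) concerning to the participant and (2) results in seeking medical attention".

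**The concern.** The Section 6.4 sentence and Section 7.1.1 cannot both describe the same interim form. One gives the health-change questions to a single arm; the other says both arms are asked about medical contacts.

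The choice matters because the second element of the adverse-event definition is that the participant sought medical attention. The follow-up questionnaires are the only structured route the protocol describes for participants to report this. If one arm is asked and the other is not, a difference in event counts may reflect the form rather than the participants. The trial compares coaching toward more activity with no coaching, in a cardiac population. A reader of the results will look at events by arm even though the main outcomes are activity and fitness.

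**Working it through.** No arithmetic applies. The check sets the sections side by side for each follow-up assessment.

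| Assessment | Sentence describing the form | Item list | Section 7.1.1 |
|---|---|---|---|
| Interim, weeks 8-12 (6.4) | Health-change questions tied to the comparison arm | Item present, no arm restriction | Both arms asked |
| Post-intervention, weeks 20-26 (6.5) | No arm restriction on this item | Item present, for participants | Both arms asked |
| 6 months, weeks 46-50 (6.7) | Same form as interim | Item present, no arm restriction | Not named |

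1. **Interim.** One sentence points to the comparison arm only. The list directly below it and Section 7.1.1 point to both arms. No other section says which governs.

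2. **Post-intervention.** There is no conflict. Sections 6.5 and 7.1.1 agree that all participants are asked.

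3. **6 months.** The form is defined as the interim form, so it inherits whichever reading is used there. The Section 6.7 list favours both arms. Section 7.1.1 cannot settle it, because it names only the interim and post-intervention questionnaires.

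4. **Is coach contact an equivalent source?** Section 5.4 schedules 8 sessions: weeks 1 to 4, then weeks 6, 8, 12 and 20. Six of the eight fall by week 8. The session descriptions in Section 5.4.1 contain no standing symptom or health question, and Section 7.1.1 describes what coaches do once a symptom has been reported. There is no session between weeks 12 and 20, and none is scheduled after week 20, so this source is absent at weeks 46-50. It is also unavailable to the comparison arm throughout, so it differs from a common questionnaire whether it captures more or less.

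5. **Other sources.** Section 7.1.1 says medical events during the study are documented in general, including unplanned cardiology visits, urgent or emergency care and unplanned admissions, with no arm limit. It names no systematic participant-report source for these other than the questionnaires. Section 7.5 has the DSMB reports count participants who contacted their cardiologist over symptoms in the treatment arm, and names no matching count for the comparison arm.

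6. **Recall period.** The Section 6.4 sentence refers to changes since baseline. Sections 6.5 and 6.7 state no period, so it is not clear that the post-intervention form would recover interim events missed in one arm.

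One assumption runs through this: that the health-change item in the lists is the same thing as the Section 7.1.1 question about medical attention. The questionnaire wording is not in the document.

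**The case against.** The strongest reply is that this is a drafting slip. One awkward sentence stands against its own item list, the lists in Sections 6.5 and 6.7, and the safety section. Nothing presents arm-specific safety questions as a design choice. Most readers would conclude that both arms were meant to be asked, and the forms may have been built that way. This stands, and it makes the harm conditional. It does not remove the conflict, because the sentence is the only text in Section 6.4 that says who gets these questions, and a person building the survey could follow it.

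The second reply is that the intervention arm is watched more closely, not less. It has repeated coach contact, a procedure for new cardiac symptoms, a DSMB count and the post-intervention form. This also stands in part. A reader might infer that intervention-arm events would come only from what participants tell coaches. The documents do not support that, since Section 7.1.1 documents medical events generally and Section 6.5 asks every participant later. A reader might also infer that events in the coached arm would be undercounted and a safety signal missed. That is not supported either: fuller capture through coaches is just as possible, so the direction is unknown.

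The third reply is that Section 7.9 plans no by-arm comparison of adverse events. That is correct. The activity, sedentary-time, fitness and feasibility analyses do not use the item. The point therefore concerns safety description and the judgement in Section 7.4 of whether serious events are related to the intervention, not any planned estimate or test.

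**Conclusion.** The contradiction is real and nothing elsewhere in the document resolves it. If the Section 6.4 sentence is followed, structured self-report of medical contacts differs by arm at interim and, through Section 6.7, possibly at 6 months, and by-arm adverse-event counts are not comparable. If Section 7.1.1 and the unrestricted lists are followed, both arms are asked alike at interim; the wording still needs correcting, and Section 7.1.1 remains silent on 6 months.

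No size can be attached. The documents give neither an event rate nor a capture rate for any source, and the sign of any distortion is undetermined. The conclusion rests on the text alone and on the assumption, noted above, that the listed item carries the medical-attention question. It is worth correcting because it is an operational data-collection rule that bears on the adverse-event definition and costs almost nothing to put right. It does not threaten the primary or secondary outcomes.

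**What to change.** Reconcile Sections 6.4, 6.7 and 7.1.1:

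- State in Section 6.4 that both arms receive the same health-change items, and remove the wording that ties them to the comparison arm.
- State the same in Section 6.7, and add the 6-month questionnaire to the sentence in Section 7.1.1.
- Use the same item wording and one defined recall rule, applied alike to both arms, at interim, post-intervention and 6 months.
- Base any by-arm event summary on this common source, and list symptoms reported to coaches separately.
- If arm-specific forms have already been used, say which arm received which form and at which assessment, and caveat by-arm counts accordingly.

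The cost is a short protocol correction with IRB approval and, if the forms did differ, a few extra questionnaire items for the intervention arm. No visit or staff need be added.
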